Personalized Recommendations for Acute Kidney Injury (AKI) Care Using a Kidney Action Team: A Randomized Trial

NCT04040296
Protocol Document
Document Date: 7 May 2024

CLINICAL STUDY PROTOCOL

Protocol Title: Personalized Recommendations for Acute Kidney Injury (AKI) Care Using a Kidney Action Team: A Randomized Trial

Principal Investigator

[name]

Protocol Version

7 May 2024

version 4

REVISION HISTORY:

Revision #	Version Date
Original	October 1, 2021
V2	February 24, 2023 Update to 7.5 Data Collection
V3	April 5 th , 2023 Update 5.3.2 Eligibility Criteria
V4	May 7 th , 2024 Update to 5.2.2 Secondary Outcomes and 7.5 Data Collection

Study Personnel

Principal Investigator

[name]

Email: [contact]

Key Study Personnel:

[name]

Email: [contact]

[name]

Email: [contact]

Synopsis

Primary Objective

This is a clinical trial designed to determine whether personalized recommendations for the workup and treatment of patients with Acute Kidney Injury (AKI) will improve the rates of AKI best practices and reduce the rates of inpatient dialysis, inpatient mortality and AKI progression in a hospitalized population.

Study Duration

We anticipate approximately 36 months in which patients are randomized and data is collected, followed by 6 months of data analysis activities and publication.

Study Design

This is a randomized, controlled, single-blind, multicenter clinical trial.

Study Population

Adult inpatients within the Yale New Haven Health System who meet the following criteria:

Inclusion Criteria:

1. Adults \geq 18 years admitted to a participating hospital
2. Stage 1 Acute Kidney Injury as defined by KDIGO creatinine criteria:
 - a. 0.3 mg/dl increase in inpatient serum creatinine over 48 hours OR
 - b. 50% relative increase in inpatient serum creatinine over 168 hours

Exclusion Criteria:

1. Admission to hospice service or comfort measures only order
2. Recipient of a solid organ transplant
3. Immediate dialytic indication determined by the following:
 - a. $K \geq 7$ meq/L
 - b. Acute ingestion of dialyzable toxin
 - c. Refractory volume overload
 - d. $BUN > 150$ mg/dL
 - e. $pH < 7.15$ despite ventilatory support
4. Pre-existing CKD stage 5 or ESKD
5. Initial hospital creatinine > 4.0 mg/dl
6. Nephrology already consulted
7. Status post nephrectomy (partial or radical) during index admission

Number of Participants

The study will enroll 4,000 individuals.

Number of Study Sites

The study will occur across two health systems and 7 study sites.

1) The Yale New Haven Health System, comprising five hospitals in Connecticut and Rhode Island: Yale New Haven Hospital, Bridgeport Hospital, Greenwich Hospital, Lawrence and Memorial Hospital, and Westerly Hospital.

2) Two hospitals in the Johns Hopkins Hospital System: Johns Hopkins Medical Center and Johns Hopkins Bayview

Primary Outcome Variables

The primary outcome will be a composite of progression of AKI, Dialysis, and death at 14 days post randomization or at hospital discharge, whichever comes first. Progression of AKI is defined as a higher KDIGO-creatinine stage than that present at the time of randomization. Dialysis is defined by the receipt of hemodialysis, continuous renal replacement therapy, or peritoneal dialysis. Isolated ultrafiltration treatments for the purpose of volume removal will not be included.

Secondary and Exploratory Outcome Variables (if applicable)

Several secondary outcomes will be assessed as follows:

- Inpatient mortality rate within 14 days
- Inpatient dialysis rate within 14 days
- Inpatient progression of AKI within 14 days
- The percent of discrete recommendations followed within 24 hours of randomization
- The rate of kidney consult within 14 days
- Rates of discharge to hospice care

We will also perform an assessment of heterogeneity of treatment effect across the study sites, as it is possible that the benefit of the KAT depends not only on patient characteristics, but upon local resources and practices.

1 - Introduction

1.1 Introductory Statement

This is a clinical trial designed to determine whether personalized recommendations for the workup and treatment of patients with Acute Kidney Injury (AKI) will improve the rates of AKI best practices and reduce the rates of inpatient dialysis, inpatient mortality and AKI progression in a hospitalized population.

2 - Background

2.1 Clinical Experience

Acute Kidney Injury (AKI), defined as an abrupt loss in kidney function, is common, occurring in 5-20% of hospitalized patients, and carries a significant and independent risk of inpatient mortality of up to 20% in some studies, even with small increases in serum creatinine concentration.¹⁻⁶ If left untreated, AKI may significantly increase the risk of chronic kidney disease, the need for dialysis, and long-term mortality.⁷⁻⁹

Despite such effects on morbidity and mortality, the incidence of AKI is increasing and clinical trials have yet to find an intervention that can be broadly implemented as an AKI treatment.¹⁰⁻¹¹ Thus, international guidelines for the treatment of AKI focus on "best practices" that include appropriate management of drug dosing, the avoidance of kidney-toxic exposures, and careful assessment of fluid and electrolyte balance.² Management relies on three pillars of care: recognition, diagnostic workup, and a patient-specific treatment plan. Early recognition of AKI and early nephrologist involvement may improve clinical outcomes.³ However, AKI, which is often asymptomatic, is frequently overlooked in a variety of hospital settings.^{1,12-13} In a previous study, we showed that only 43% of patients at a tertiary care academic hospital had documentation of their AKI in the medical record, and that missed documentation was associated with increased mortality after adjusting for admission type and severity.¹⁴ Perhaps more concerning, our group and others have shown that patients often continue to be exposed to kidney-toxic medication after AKI onset.¹⁵⁻¹⁶ Other AKI "best practices", such as urinalysis and further laboratory work-up, occur inconsistently and in a small minority of patients with AKI.¹⁷⁻¹⁹

Previous studies by our group have focused extensively on increasing provider awareness and recognition of AKI. Our group conducted a randomized clinical trial testing the efficacy of electronic alerts for AKI.²⁰⁻²¹ This trial randomized 2,373 patients with AKI to usual care, or to an alert group in which a single alert was sent to the patient's primary provider. This alert was to make providers aware of the presence of AKI, however, it did not describe or offer specific actions a provider could take in response to the alert. We demonstrated clinical equipoise regarding the effectiveness of such alerting, as there was no improvement in the rates of AKI progression, dialysis or mortality among those in the alert group.

Rather than simply making providers aware of AKI, it may be beneficial to provide them with actionable items to aid in the care of their patients. Because of the heterogeneity of both the AKI patient population and AKI etiology, diagnostic and treatment plans must be highly individualized. Such plans must consider many facets of care, including changes to and careful monitoring of prescribed medications, optimization of hemodynamics, and management of complications. Despite the apparent complexity, we believe that individualized plans are amenable to highly protocolized interventions that can be delivered in a timely manner. Our aim in this study is to determine, through a randomized multicenter clinical trial, if personalized recommendations for the work-up and treatment of AKI will improve patient outcomes. Patients with AKI will be identified in real-time, upon which a "Kidney Action Team" will be alerted. The Kidney Action Team will be composed of an

advanced practitioner and a pharmacist, and overseen by a nephrologist, and trained to provide real-time recommendations for AKI work-up and management within one hour of AKI onset. Patients will be randomized to either receive usual care, or to an active intervention group in which the recommendations of the Kidney Action Team are delivered to the patient's primary care team. Our primary outcome will be a composite of AKI progression, dialysis and death at 14 days post-randomization, while process outcomes will focus on the amount of recommendations implemented within 24 hours of delivery. The highly protocolized and objective nature of AKI recommendations will allow for multiple independent Kidney Action Teams across multiple study sites, and, should this intervention prove successful, will provide a highly generalizable model for easy integration into other health systems. Further, because of their highly algorithmic nature, the recommendations are amenable to automation, and our results may warrant future research to create and validate an automated clinical decision support system that will efficiently identify AKI patients and provide highly individualized and timely treatment plans without the need for a Kidney Action Team.

2.2 Background/prevalence of research topic

Rapid response teams have proliferated, but no rapid response team for AKI has been evaluated. In 2008, the Joint Commission National Safety Goal required hospitals to implement systems to enable staff to directly request the aid of specially trained individuals when a patient's clinical appearance is worsening.²² The concept of the "rapid response team" was quickly adopted, with most hospitals in the US enacting at least some of the principles. Goals of the team are generally to prevent clinical deterioration, avoiding out-of-ICU intubation or cardiac arrest. Meta-analyses suggest that in that capacity, they have been successful, though whether they decrease overall mortality is unclear.²³⁻²⁴ To date, no rapid response teams focused on AKI have been developed, though some small studies looking at early renal consult (within 24 hours) suggest some benefit.^{3,25} To be able to provide true rapid response for AKI (i.e. within 30 minutes), an automated AKI detection system and a well-trained "Kidney Action Team" needs to be in place. We have pioneered the use of automated AKI alerts, and have a highly accurate electronic monitoring system in place across the study hospitals. In contrast to conventional rapid response teams, Kidney Action Teams can operate remotely, greatly expanding their reach and reducing associated costs. This may be of particular benefit in rural healthcare settings, where access to nephrology expertise is limited.

3 - Rationale/Significance

3.1 Problem Statement

It is unclear whether early, personalized recommendation for AKI diagnosis and treatment will meaningfully improve clinical outcomes among hospitalized patients.

3.2 Purpose of Study/Potential Impact

The purpose of this study is to evaluate the impact of a Kidney Action Team - a remote group of individuals who, by receiving real-time AKI alerts, can provide personalized initial recommendations for treatment and management. If the teams are shown to be successful, health systems may consider adopting this approach to mitigate the devastating downstream effects of AKI which include chronic kidney disease, dialysis, and death.

3.3 Potential Risks and Benefits

3.3.1 Potential Risks

We consider the study to be minimal risk, as we are synthesizing information already available to providers in the medical record and offering recommendations for care that would already otherwise be available to the patient. These recommendations are not experimental, and represent best practices for AKI care. Potential risks are as follows:

- Inattention to AKI: A general risk of providing recommendations in a randomized fashion is the possibility that providers, who care for multiple patients each day regardless of randomization status, will become accustomed to receiving recommendations for their AKI patients and thus become inattentive to those patients in the control arm for whom they receive no recommendations. We will mitigate this effect by reminding providers in the recommendation note that this is part of a randomized trial and that recommendations are not sent for all patients who develop AKI. Pre-trial and periodic provider outreach will also be conducted to emphasize this point.
- Overtreatment: If the delivery of personalized recommendations affects physician behavior, then patients randomized to the intervention arm may be more likely to undergo certain tests or interventions, such as additional testing, than those in the control arm. While these interventions fall into the standard of care, the recommendations are made by a Kidney Action Team without direct patient interaction. Therefore, it is possible that some interventions may not be appropriate, may not benefit the patient, and may incur additional costs to the patient. We will make clear in the Kidney Action Team note that none of the recommendations are mandated, and that the providers clinical decisions should be paramount to any recommendation. Treating physicians are to use their own clinical judgement when making clinical decisions about these interventions.
- Undertreatment/lack of follow up: Patients randomized to the intervention group may, based on recommendations, have certain kidney-toxic medications discontinued. It is possible that in some unique situations, discontinuation of medication may engender more risk (for example, discontinuation of a proton pump inhibitor in a

patient at high risk for gastrointestinal bleeding). Further, it may be incorrectly assumed by the primary care teams that the Kidney Action Team will follow up with further recommendations or with test results, and thus not follow up themselves. We will attempt to prevent this through our pre-trial and periodic educational efforts where we will remind primary providers of the nature of the trial, that it is still best to use their own clinical judgement when deciding to follow recommendations, and that recommendations only occur once, with no follow up from the Kidney Action Team. This will also be made clear in the Kidney Action Team note, which will indicate that the KAT will not follow-up on results of tests, and if more assistance is needed a formal renal consult should be called.

- As with all studies where PHI is collected, loss of privacy is at risk for subjects. We will limit this risk through our use of an entirely electronic data collection system and our data security plan. To minimize loss of privacy to subjects, all patient data will be kept on a secure, HIPAA-compliant server with 2-factor authentication, accessible only from within the Yale firewall, or via VPN protocols, and only by study personnel. In addition, at the time of data acquisition, a unique study ID number will be assigned to each patient. All PHI will be linked to this study ID number in a database that is separate and distinct from the primary dataset which includes clinical information. This linking dataset will be maintained on a separate HIPAA-compliant server and will only be accessible by the study investigators.

3.3.2 Potential Benefits

Subjects may directly benefit from participation in the study because their care teams may be more acutely aware of their medical condition and may provide more personalized, attentive care based on recommendations delivered from the Kidney Action Team. Should our paradigm of personalized treatment plans prove successful in improving patient outcomes, a broader implementation could provide benefits to society at large.

4 - Study Objectives

4.1 Hypothesis

A composite of progression of AKI, dialysis, and death will be significantly lower among patients randomized to receive Kidney Action Team recommendations compared to those randomized to usual care.

4.2 Primary Objective

This is a clinical trial designed to determine whether personalized recommendations for the workup and treatment of patients with Acute Kidney Injury (AKI) will improve the rates of AKI best practices and reduce the rates of inpatient dialysis, inpatient mortality and AKI progression in a hospitalized population.

5 - Study Design

5.1 General Design Description

This is a randomized, controlled, multicenter clinical trial to determine the efficacy of the delivery of personalized recommendations for the treatment of AKI in reducing clinical outcomes of AKI progression, dialysis, and death in hospitalized patients. Patients who develop AKI will be identified in real time and randomized to either usual care or to the active intervention group, in which the primary care team receives individualized recommendations for AKI treatment from a trained Kidney Action Team.

5.1.1 Study Date Range and Duration

We anticipate approximately 36 months in which patients are randomized and data is collected, followed by 6 months of data analysis activities and publication. The entire study will take place over the course of 4 years.

5.1.2 Number of Study Sites

The study will occur across two study sites.

- 1) The Yale New Haven Health System, comprising five hospitals in Connecticut and Rhode Island
- 2) Two hospitals within the Johns Hopkins University Hospital System: Johns Hopkins Medical Center and Johns Hopkins Bayview.

5.2 Outcome Variables

5.2.1 Primary Outcome Variables

Composite of progression of AKI, dialysis, and death at 14 days post randomization or at hospital discharge. Progression of AKI is defined as a higher KDIGO-creatinine stage than that present at the time of randomization. Dialysis is defined by the receipt of hemodialysis, continuous renal replacement therapy, or peritoneal dialysis. Isolated ultrafiltration treatments for the purpose of volume removal will not be included.

5.3 Study Population

We will enroll adult inpatients in the Yale New Haven Health System and Johns Hopkins University Health System who develop Stage 1 AKI based on KDIGO creatinine criteria and who meet all inclusion and exclusion criteria described below.

Yale health system hospitals include Yale New Haven Hospital, Bridgeport Hospital, Greenwich Hospital, Lawrence and Memorial Hospital, and Westerly Hospital. Johns Hopkins sites include Johns Hopkins University Hospital and Johns Hopkins Bayview Campus. Sites will use a central IRB (BRANY).

5.3.1 Number of Participants

We determined the overall sample size of this study based on the clinical composite outcome of progression of AKI, Dialysis, and Death. The baseline rate of this outcome is 21% based upon our preliminary data, and we felt that a relative 20% improvement (to 16.8%) would represent a clinically meaningful difference. In order to have 90% power to detect such a difference (or greater) if it exists at an alpha of 0.05, we would need to enroll 1,824 patients in each group, for a total of 3,648 in the study. Given concerns about contamination across the study arms (see III.J.9), we have increased this recruitment target by approximately 10% to a total of 4000 individuals. Enrollment of 4000 individuals will also allow us to detect a difference in the rate of adherence to recommendations of 10% of one standard deviation at an alpha of 0.05, which is ample power to determine if the provision of these recommendations change provider behavior.

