6.1 Treatment - Device

6.1.1 Intended use for the device

Kidney Action Team Recommendations

Dedicated and trained Kidney Action Teams (KATs) will each consist of an advanced practitioner and a pharmacist and will be supervised by a nephrologist. KATs will be available 24 hours a day, 7 days a week, barring extenuating circumstances. The KAT will be notified, in real-time, of all randomized patients at their site who meet enrollment criteria via an automated electronic health record system. The KAT will be tasked with providing individualized recommendations for AKI workup and treatment based on best practices identified within several kidney domains. Recommendations will be created for each randomized patient, however, they will only be delivered to the primary care teams of those patients who have been randomized to the active intervention group. This strategy allows for both the blinding of the KAT as well as a comparison in the proportion of recommendations implemented between the control and intervention groups.

Recommendations for those in the intervention group will be made and delivered within one hour of AKI alert via a specialized note (Appendix 1) that is entered into the patient's chart and flagged for cosigning by the covering primary physician (i.e., the person signed on to EPIC as the patient's covering provider for that shift).

We have designed the recommendations to be limited to specific domains of AKI diagnosis and treatment in order to minimize the variability in recommendations across members of the Kidney Action Teams and to allow for timely recommendations to be made. These domains include potassium management, acid/base management, fluid management, drug redosing and cessation, and diagnostic work-up. We have also included a set of universal recommendations that will be delivered to all patients randomized to the intervention group, as we feel these to be a necessary component of a standard work-up for any AKI patient.

Universal AKI recommendations will be recommended if not yet performed in the 48 hours prior to randomization and include:

- Obtaining a urinalysis
- Obtaining a urine sodium, potassium, chloride, creatinine measurement
- Obtaining a post-void residual measurement or renal ultrasound to rule out obstruction
- Avoiding new nephrotoxic exposures
- Measuring serum creatinine at least every 24 hours during the inpatient stay
- Strict measurement of fluid input and output

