6.1.3 Method of Assignment/Randomization

Randomization will be performed within REDCap using a computer-generated randomization table which will use permuted blocks (of 4, 6 and 8 individuals). Randomization will be stratified by study hospital.

The Kidney Action Team will create recommendations for all patients that meet eligibility criteria, regardless of randomization status, which will preserve their blinding.

(Recommendations will only be delivered to patients in the intervention group). Providers and patients will not be blinded. Study investigators and analysts will be blinded to randomization status.

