6.4 Statistical Method

6.4.1 Statistical Design

We will compare rates of the primary outcome of progression of AKI, dialysis and death using the Cochrane-Mantel-Haenszel chi-square test, accounting for stratification by hospital. We will average proportion of recommendations followed within 24 hours between the intervention and control group using the Van Elteren test to account for stratification by hospital.

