6.4.2 Sample Size Considerations

We determined the overall sample size of this study based on the clinical composite outcome of progression of AKI, Dialysis, and Death. The baseline rate of this outcome is 21% based upon our preliminary data, and we felt that a relative 20% improvement (to 16.8%) would represent a clinically meaningful difference. In order to have 90% power to detect such a difference (or greater) at an alpha of 0.05, we would need to enroll 1,824 patients in each group, for a total of 3,648 in the study. Given concerns about contamination across the study arms (see III.L.9), we have increased this recruitment target by approximately 10% to a total of 4000 individuals. Table 2 shows a breakdown of recruitment by study site. Given the fact that this trial will operate under a waiver of informed consent, and our prior track record in this space, we expect full accrual across both sites within 3 years. Enrollment of 4000 individuals will also allow us to detect a difference in the rate of adherence to recommendations of 10% of one standard deviation at an alpha of 0.05, which is ample power to determine if the provision of these recommendations change provider behavior.

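### Does the rise from 3,648 to 4,000 for contamination need a stated dilution and a stated power at 4,000?

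*Combined protocol and SAP*

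**What the plan says.** Sections 5.3.1 and 6.4.2 give the same calculation. On the control rate: "The baseline rate of this outcome is 21% based upon our preliminary data". A relative reduction of 20%, to 16.8%, is taken as clinically meaningful. With 90% power and alpha 0.05 this gives 1,824 per group, 3,648 in all.

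Both sections then enlarge the trial. In section 5.3.1, "we have increased this recruitment target by approximately 10% to a total of 4000 individuals", with a pointer to III.J.9 for the concern about contamination. Section 6.4.2 has the same sentence with a different pointer: "Given concerns about contamination across the study arms (see III.L.9), we have increased this recruitment target by approximately 10" per cent, to 4,000. The protocol numbers its sections 1 to 7 with decimals, so neither label leads anywhere in it.

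The one detectability statement made at 4,000 concerns a process measure. The trial is said to be able to "detect a difference in the rate of adherence to recommendations of 10% of one standard deviation at an alpha of 0.05". This is called ample power, without a figure. Section 6.4.1 compares that measure between arms "using the Van Elteren test to account for stratification by hospital".

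Two features of the design bear on contamination. Section 3.3.1 refers to "providers, who care for multiple patients each day regardless of randomization status", and section 6.1.3 states: "Providers and patients will not be blinded".

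**The concern.** Randomization is by patient, while the intervention acts on clinicians who look after patients in both arms and know which of them had a note. Advice learned on one patient can carry over to a control. Some dilution of the effect is therefore plausible, and the protocol itself raises it as the reason for the last step in the sample size.

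A reader would expect that step to rest on a stated loss of effect and to end with a stated power. Neither appears, and the pointers that might lead to them disagree. There is also a trap in the round figure. An increase of about 10% may be read as cover for 10% contamination, but required sample size grows roughly with the inverse square of the remaining effect, so it covers much less. If the trial were null, one could not say from this document how much contamination it had been designed to withstand.

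**Working it through.** **Inputs.** Control rate 21%, intervention rate 16.8%, power 90%, alpha 0.05, 1,824 per group and 4,000 in total, all from sections 5.3.1 and 6.4.2. Equal groups of 2,000 are taken from the equal split of the base calculation. Two-sided testing is not stated, but it reproduces the plan's figure; a one-sided test would give 1,487 per group.

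**The plan's own figure.** Pooled-variance formula for two proportions, with p̄ = (0.21 + 0.168)/2 = 0.189:

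n = [1.960 × √(2 × 0.189 × 0.811) + 1.2816 × √(0.21 × 0.79 + 0.168 × 0.832)]² / 0.042²

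= (1.0852 + 0.7085)² / 0.001764 = 1,823.96, so 1,824 per group and 3,648 in total. It reproduces.

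**The increase.** 4,000 − 3,648 = 352, and 352/3,648 = 9.65%. Also 3,648 × 1.10 = 4,012.8, which fits a rounded 10%.

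**Power at 4,000 without dilution.** Power = Φ([0.042 × √2,000 − 1.0852] / 0.5529) = Φ(1.4345) = 92.4%. No input beyond the printed ones is needed.

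**Power with dilution.** The documents give no rate, so a range is assumed. Let c be the share of the 4.2-point difference that is lost. On the control side the control rate becomes 21% − c × 4.2 points; on the intervention side the intervention rate becomes 16.8% + c × 4.2 points. The same power formula gives (control side / intervention side):

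| c (assumed) | Power at 3,648 | Power at 4,000 |
|---|---|---|
| 0% | 90.0% | 92.4% |
| 5% | 87.0 / 86.7% | 89.8 / 89.6% |
| 10% | 83.4 / 82.8% | 86.6 / 86.0% |
| 15% | 79.2 / 78.1% | 82.7 / 81.8% |
| 20% | 74.4 / 72.9% | 78.2 / 76.8% |

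The added patients buy 2.4 points of power with no dilution and about 3 to 4 points at 10% to 20%. At 4,000, power reaches 90% at c = 4.7 / 4.3% and 80% at c = 18.1 / 16.9%. The inverse-square shortcut agrees: 1 − √(3,648/4,000) = 4.5%. Holding 90% power at 10% control-side dilution would take about 4,468 patients.

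**Adherence.** For 0.1 SD with 2,000 per group, a two-sample z-test has power Φ(0.1 × √(2,000/2) − 1.96) = 88.5%. A rank test has somewhat less. At assumed efficiencies of 0.955 and 0.864, the same formula with 2,000 multiplied by the efficiency gives 87.1% and 83.6%. The word ample is fair across that range.

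**What these figures leave out.** They ignore stratification by hospital. They also use the full 0.05 at the final look, whereas section 7.9 mentions an interim analysis with no alpha given. Under assumed final-look levels of 0.049 and 0.0294, undiluted power at 4,000 is 92.3% and 88.8%.

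**The case for a change.** The strongest case for acting is that contamination is the protocol's own stated worry, that it alone explains the last 352 patients, and that the correction would cost a sentence or two. A design assumption ought to be on record before the results are known, and comparing adherence between arms afterwards does not supply one. The facts behind this stand: no rate, no power at 4,000, and two pointers that conflict.

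The harm claimed from them is smaller than it looks.

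- The target difference is printed, 21% to 16.8%, and 3,648/4,000 = 91% of the enrolment rests on a calculation that can be checked. Only the choice of roughly 10% cannot.
- No promise is broken. The plan nowhere says that 90% power survives contamination.
- The pointers use a numbering foreign to this protocol, and section 6.4.2 also cites a Table 2 that is not in the text. Probably the passage was carried over from another document, which may hold the rate. What is shown is a broken cross-reference, not the absence of an assumption.
- Section 3.3.1 is weak support for dilution. It describes clinicians becoming inattentive to control patients, which would worsen control outcomes and widen the difference.
- A table of assumed dilution levels placed in the protocol would not explain why 10% was chosen. It would only put a reviewer's assumptions where the sponsor's should be.

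**Conclusion.** No change follows. The base calculation is correct, the increase is a modest margin on top of it, and the missing power at 4,000 can be worked out from what is printed: about 92.4% without dilution, assuming equal arms, a two-sided 0.05 and no alpha spent at an interim look. Under the assumed dilution models the margin offsets a loss of about 4% to 5% of the absolute difference, and power stays above 80% until about 17% to 18% is lost. Nothing in the documents shows that dilution would be larger than this, or how large it would be.

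The differing pointers are a clerical slip. The missing dilution rate is a gap in reporting that leaves the enrolment target, the stratified primary test and the reading of the estimate as they are. Whether the arms separated in practice will be seen from the planned adherence comparison, since recommendations are written for every randomized patient but delivered in one arm only (section 6.1.1). Anyone interpreting a null result should simply not take the increase of about 10% as protection against 10% contamination.
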